14.5 The MRI endpoints

As listed in Section 3.5.4, the MRI endpoints refers to changes in gray matter volume, compound ventricular volume, FA and MD in corpus callosum and cerebral white matter, SWI in cerebral white matter and basal ganglia.

To assess the PD effect of SOBI003 on MRI, linear models are used to model the change from baseline in MRI as dependent variable, for both logged MRI and untransformed MRI, and baseline level and age as continuous covariates, and accumulated dose (including the FIH study) as covariate and sex as factor. The analyses are conducted for each assessment time point: week 52 and 104.

In addition, linear analyses with MRI levels, both logged MRI levels and untransformed MRI levels, as dependent variable, and baseline level and age as continuous covariates, and accumulated dose as covariate and sex as factor will be performed across all assessments (including the FIH study), with assessment as a repeated factor.

14.6 Exploratory endpoints

Continuous variables are summarized using the number of patients, the mean, the standard deviation, the median, the minimum value, and the maximum value. Categorical variables are summarized using frequency counts and percentages.

14.7 Other efficacy endpoints

Endpoints relating to the neurocognition, liver and spleen volume, QoL, language, motor function and sleep pattern are summarized using descriptive statistics.

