Immunogenicity is summarized using frequency counts and percentages by dose level and will be evaluated regarding antibody prevalence (pre-existing antibodies), antibody incidence, titer and boosting following dosing, impact on PK and PD.

Adaptive behavior will be analyzed with the same repeated measures model as DQ, but adapted for one group (i.e. no treatment\*visit interaction term).

To assess the PD effect of SOBI003 on MRI, linear models are used to model the change from baseline in MRI as dependent variable for both logged MRI and untransformed MRI, and baseline level and age as continuous covariates, and accumulated dose (including the FIH study) as covariate and sex as factor. The analyses will be conducted for each assessment time point: week 52 and 104.

In addition, linear analyses with MRI levels (both logged MRI levels and untransformed MRI levels), as dependent variable, and baseline level and age as continuous covariates, and accumulated dose as covariate and sex as factor will be performed across all assessments (including the FIH study), with assessment as a repeated factor.

Endpoints relating to other neurocognitive variables, liver and spleen volume, QoL, language, motor function and sleep pattern are summarized using descriptive statistics.

PK results are presented by dose level using descriptive statistics. In addition, results are presented by demographic characteristics, e.g., age-group and bodyweight, as applicable.

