#### **9.4.4.2 Secondary endpoints and additional key secondary endpoints**

To assess the PD effect of SOBI003 on HS levels in CSF, serum and urine, linear models are used to model the change from baseline in HS levels as dependent variable, for both logged HS levels and untransformed HS levels, and baseline level and age as continuous covariates, and accumulated dose as covariate and sex as factor. The analyses are conducted for each assessment time point. In addition, linear analyses with HS levels, both logged HS levels and untransformed HS levels, in CSF, serum and urine, as dependent variable, and baseline level and age as continuous covariates, and dose and sex as factors will be performed across all assessments, with assessment as a repeated factor.

Adaptive behavior will be analyzed with the same repeated measures model as DQ, but adapted for one group (i.e. no treatment\*visit interaction term), the SOBI003 group.

PK results are presented by dose level using descriptive statistics. In addition, results are presented by demographic characteristics, e.g., age-group and bodyweight, as applicable.

Immunogenicity is summarized using frequency counts and percentages by dose level. To assess the PD effect of SOBI003 on MRI, linear models are used to model the change from baseline in MRI as dependent variable, for both logged MRI and untransformed MRI, and baseline level and age as continuous covariates, and accumulated dose (including the FIH study) as covariate and sex as factor. The analyses are conducted for each assessment time point i.e. Weeks 52 and 104.

In addition, linear analyses with MRI levels, both logged MRI levels and untransformed MRI levels, as dependent variable, and baseline level and age as continuous covariates, and accumulated dose as covariate and sex as factor will be performed across all assessments (including the FIH study), with assessment as a repeated factor.

Endpoints relating to the neurocognition, adaptive behavior, liver and spleen volume, QoL, language, motor function and sleep pattern are summarized using descriptive statistics.

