3.2 Key secondary objectives

- To evaluate the efficacy of SOBI003 on neurocognitive function, as compared to untreated MPS IIIA patients from a NH control.
- To evaluate the effect of SOBI003 on HS levels in CSF

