3.5.3 Key secondary endpoints

Study efficacy evaluation will primarily be based on:

- Change from baseline at Week 104 in Development Quotient (DQ) as assessed by the Bayley Scales of Infant and Toddler Development®, third edition (BSID-III) cognitive subtest or the Kaufman Assessment Battery for Children, Second edition (KABC-II)
- Change from baseline at Week 104 in CSF HS

Additional key secondary endpoints are:

- Change from baseline at Week 52 in Development Quotient (DQ) as assessed by the Bayley Scales of Infant and Toddler Development®, third edition (BSID-III) cognitive subtest or the Kaufman Assessment Battery for Children, Second edition (KABC-II)
- Change from baseline at Weeks 52 and 104 in Age Equivalent (AEq) as assessed by the Bayley Scales of Infant and Toddler Development®, third edition (BSID-III) cognitive subtest or the Kaufman Assessment Battery for Children, Second edition (KABC-II)
- Change from baseline at Week 52 in CSF HS

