4.1 Overall study design and plan

This is an open, single-arm, multicenter extension study to assess the long-term safety, tolerability and efficacy of SOBI003 in pediatric MPS IIIA patients who previously participated in the (FIH) SOBI003-001 study. Patients completing the FIH study will be offered to participate in the extension study. Please refer to Figure 1 for an overview of the study design. A published natural history study (referred to as the NH study in the present document) is used as external control (**Error! Reference source not found.**). Neurocognitive and adaptive behavior data assessed in the extension study at Week 52 and Week 104 following start of treatment will be compared to available natural history data within the target study population. The natural history population for comparison consists of 14 patients with a rapid progressive MPS IIIA disease and a baseline age of 12 to 72 months.

[figure not shown]
As the FIH study has a sequential, ascending, multiple-dose design, the first patients will enter the extension study (SOBI003-002) before finalization of the FIH study. When entering the extension study, these patients will receive the highest dose that has been declared safe by the

SRC in the ongoing FIH study. Patients enrolled in Cohort 1 of FIH may thus be switched to the dose applied in Cohort 2 or Cohort 3, depending on safety clearance by the SRC. If a patient is initially switched to the dose applied in Cohort 2, the patient may subsequently later be switched to the dose applied in Cohort 3. Depending on recruitment rate in the FIH study, a patient enrolled in Cohort 1 may be directly switched to the dose applied in Cohort 3. Upon completion of the FIH study, an analysis aimed at selecting the dose for forthcoming studies will take place. Once the dose has been selected, this dose will be applied to all patients enrolled in the extension study. The Baseline in SOBI003-001 will be used as the baseline for SOBI003-002 (Figure 1).

SOBI003 is administered as weekly i.v. infusions over a period of time of 1 to 4 hours. Prior to initiation of each infusion, the patients are pretreated with a single dose of non-sedative antihistamine. If infusion-related reactions occur, then the infusion duration may be expanded up to 24 hours and supportive medication may be administered, at the discretion of the investigator.

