11.2 Baseline characteristics

Other baseline measurements that will be listed include DQ, AEQ and genotype. The listing will include the NH study as well.

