14.1 The DQ endpoint

One of the key secondary objectives is to assess the effect of SOBI003 on neurocognition, as compared to untreated MPS IIIA patients from a NH control. The key endpoint related to this

objective is the change from baseline in DQ of neurocognitive development at 104 weeks of treatment, and will be estimated by a model based contrast.

To address the efficacy objective, a repeated measure analysis will be utilized where DQ is the response variable and time, baseline age, time*baseline age and treatment*time are fixed effects and the dependency between observations within the same patient is represented by an unstructured variance-covariance matrix.

The time window is two weeks, i.e., if the assessment is more than two weeks too early or more than two weeks too late, then the DQ is set to missing for that assessment.

In the NH study, a simple linear regression model was used, i.e. with DQ as the response variable and the age of the child as dependent variable (Shapiro et al 2016). As the aim in this clinical development program is to demonstrate that treatment with SOBI003 is efficacious and the effect of treatment is dependent on the time the patient has been treated, this model needs to be adopted so that time and baseline age are factors rather than the actual age of the child (which is the sum of the baseline age and the time in study). The results from the NH study suggest that the decline in DQ is not linear across all ages, and an interaction term time*baseline age is planned to be included in the model to allow for such a non-linearity. Also an unstructured variance-covariance matrix is planned to be used to account for the dependency between observations within the same patient. As a further justification for the model, it should be noted that time, baseline age and time*baseline age are all significant factors in the NH study.

To represent the treatment effect without constraint to a specific relation across visits, a term treatment*time is planned to be included in the model. This effect is used to judge the treatment effect. The null hypothesis of no treatment effect will be tested with a significance test for the treatment*time-effect in the second step of the multiple testing procedure (see Section 14.3). The difference between 104 weeks and baseline will be used as the contrast of interest for the test.

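### Cognitive age-equivalent score is a key secondary endpoint under an objective of comparison with natural history patients, but is planned as descriptive only, so no age-equivalent difference from control is estimated

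*SAP*

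**What the plan says.** SAP 3.2 words the objective as a comparison: "To evaluate the efficacy of SOBI003 on neurocognitive function, as compared to untreated MPS IIIA patients from a NH control". Among the additional key secondary endpoints, SAP 3.5.3 lists "Change from baseline at Weeks 52 and 104 in Age Equivalent (AEq) as assessed by the Bayley Scales"; protocol 6.2.1 matches. SAP 4.1 says that neurocognitive data at Weeks 52 and 104 "will be compared to available natural history data within the target study population".

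The only model that uses the NH patients is in SAP 14.1, where "a repeated measure analysis will be utilized where DQ is the response variable". SAP 8.2 and protocol 9.2 place the NH patients in the full-analysis set with a parenthesis limiting this to the DQ analyses.

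Cognitive AEq has no model section. It falls under SAP 14.7: "Endpoints relating to the neurocognition, liver and spleen volume, QoL, language, motor function and sleep pattern are summarized using descriptive statistics". Protocol 9.4.4.2, whose title covers the additional key secondary endpoints, has "Endpoints relating to the neurocognition, adaptive behavior, liver and spleen volume, QoL, language, motor function and sleep pattern are summarized using descriptive statistics". The synopsis is the clearest of the three: "Endpoints relating to other neurocognitive variables, liver and spleen volume, QoL, language, motor function and sleep pattern are summarized using descriptive statistics".

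**The concern.** The endpoint's rank and objective do not match its analysis. The other key secondary endpoints, DQ and CSF heparan sulfate, are modelled. So are several lower-ranked ones: serum and urine heparan sulfate, MRI and adaptive behavior. Cognitive AEq is the one key secondary endpoint without a model, and no reason is given.

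At stake is interpretation. DQ divides developmental age by chronological age, so it falls as a child grows older even if no skill is lost. A DQ difference in favour of treatment does not say, in months of skill, whether treated children gained, held or lost relative to NH. An AEq difference with a confidence interval would.

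**Working it through.** **1. The plan's own figure.** SAP 7.1 gives 9 treated and 14 NH patients, declines of 9.8 and 30.4 DQ points (difference 20.6), SD 13.0, and power of at least 80%. SAP 9 sets tests at two-sided 5%. Reading 13.0 as the SD of change:

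- Standard error = 13.0 × √(1/14 + 1/9) = 5.55.
- 20.6 / 5.55 = 3.71, and 3.71 − 1.96 = 1.75.
- Power is 96.0% (normal) or 94.2% (noncentral t), which meets the stated bound.

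This is context only. The documents give no figure for cognitive AEq, and the point does not rest on power.

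**2. Is control AEq obtainable?** SAP 9.3 defines DQ as 100 × AEq / age, so AEq = DQ × age / 100. The SAP 14.1 model needs each NH patient's DQ by visit and baseline age, and that section notes that actual age is baseline age plus time in study. AEq at each visit then follows by arithmetic. SAP 11.2 lists baseline DQ and AEq and adds "The listing will include the NH study as well".

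**3. What the DQ assumptions imply for AEq.** Inputs from SAP 7.1 are baseline DQ 58.9 and Week 104 DQ of 58.9 − 30.4 = 28.5 (NH) and 58.9 − 9.8 = 49.1 (treated, assuming the same baseline DQ). With baseline age a in months and 24 months of follow-up:

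- NH change = 0.285 × (a + 24) − 0.589 × a
- Treated change = 0.491 × (a + 24) − 0.589 × a
- Difference = 0.206 × (a + 24)
- DQ fall if AEq does not move = 58.9 × 24 / (a + 24)

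The documents give no mean baseline age, so a is an assumption. Ages 12 and 72 are the limits of the NH subgroup.

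| Baseline age (months) | NH AEq change | Treated AEq change | Difference | DQ fall with AEq unchanged |
|---|---|---|---|---|
| 12 | +3.2 | +10.6 | 7.4 | 39.3 |
| 24 | −0.5 | +9.4 | 9.9 | 29.45 |
| 36 | −4.1 | +8.3 | 12.4 | 23.6 |
| 48 | −7.8 | +7.1 | 14.8 | 19.6 |
| 72 | −15.1 | +4.7 | 19.8 | 14.7 |

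At 24 months, nearly all of a 30.4-point DQ fall is compatible with no loss of skill. At 48 months the same fall means losing almost 8 months of skill.

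**4. Would an AEq comparison be informative?** A simulation used 9 versus 14 patients, the DQ assumptions above and adjustment for baseline age. It gave power of about 79% to 91% for AEq change. It assumed a baseline DQ SD of 10 to 25 and ages uniform on 12–72 or 24–72 months, none of which the documents give.

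**The case against.** The strongest defence is that the objective is already answered. Efficacy rests primarily on Week 104 DQ and CSF heparan sulfate, and AEq is labelled additional. DQ is compared with NH by a repeated measures model with imputation, sensitivity analyses and a principal strata analysis. The treatment-by-time term also covers Week 52, so the SAP 4.1 statement is met through DQ. Descriptive handling of AEq is stated consistently in three places and may be deliberate in an extension of 9–12 patients. All of this stands, and it limits the weight of the point.

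A reader might infer more than the documents support:

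- **That the neurocognition objective goes untested against NH.** It does not; DQ tests it.
- **That nothing will show whether treated children gained skill.** Their own AEq change from baseline is summarised with n, mean, SD and SE. AEq is also DQ rescaled by a known age, not an independent measurement.
- **That SAP 14.7 states a one-group summary.** It does not. This is inferred from the full-analysis-set parenthesis; SAP 14.4 says one group explicitly where that is meant.
- **That follow-up AEq for NH patients is confirmed to be in hand.** The SAP 11.2 listing covers baseline only, and SAP 4.1 speaks of published data. Patient-level follow-up is a reasonable inference from what the SAP 14.1 model needs.
- **That 9.9 to 14.8 months measures an error.** The ages are assumed, the treated decline is a planning assumption, and a product of means is not the mean of the products.

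One technical objection shapes the fix. SAP 7.1 assumes a DQ reduction that is homogeneous across age. The AEq effect is then 0.206 × (a + 24), from 7.4 months at age 12 to 19.8 at age 72. A single AEq contrast from the main SAP 14.1 model would depend on the age mix of two non-randomised groups.

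**Conclusion.** The point holds as a mismatch between a comparative key secondary objective and a descriptive-only analysis of one of its endpoints. As written, the plan yields no cognitive AEq difference from NH and no confidence interval for it at Week 52 or Week 104. No alpha, hierarchy step or confirmatory conclusion is affected, because AEq lies outside the two-step procedure and DQ carries the test. The change is worth making, but the plan's main efficacy test does not depend on it.

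The finding rests on the text: the endpoint list, the objective, the descriptive-only wording and the full-analysis-set parenthesis. It does not rest on the month figures, which are illustrations. Feasibility rests on the inference that DQ and age are held for each NH patient at each visit.

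**What to change.** - In SAP 14.7, protocol 9.4.4.2 and the synopsis, take cognitive AEq out of the descriptive-only list. Extend the full-analysis-set parenthesis (SAP 8.2, protocol 9.2) to the cognitive AEq analyses.
- Fit the SAP 14.1 repeated measures model to AEq with the 14 NH patients, using AEq = DQ × age / 100 where AEq is not recorded.
- Report the Week 52 and Week 104 treatment differences in change from baseline with 95% confidence intervals, labelled as supportive and outside the hierarchy.
- State the common baseline age at which the contrast is evaluated, and repeat the analysis with the time × treatment × baseline age term already listed in SAP 14.1.1. The chosen age alters the treatment contrast only once that term is in the model.
- Derive missing AEq from the imputed DQ and the age at that visit, and add a sensitivity run on observed data only.

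If the sponsor prefers to keep AEq descriptive, the SAP should say why and reconcile this with the comparative objective. The cost is SAP and protocol wording and a few extra model runs, with no new assessments and no alpha. The estimate will be imprecise with about 9 versus 14 patients.

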14.8 Subgroup Analyses

In order to examine the uniformity of the treatment effect across subgroups, additional exploratory statistical analyses will be performed on the DQ. The subgroups will be categorized according to:

- Baseline DQ
- Baseline AEq
- Sex (male, female)

The corresponding factors and treatment interactions will be included in the model, one at a time due to the small sample size.

No formal hypothesis tests will be performed.

14.9 Analysis of the subpopulation to be included in the future primary analysis population

The primary analysis will be repeated for the subgroup of subjects that will be included in the Phase III study (see Section 17), i.e., the subpopulation of the FAS patients who are up to 30 months of age and in the FIH study was initially assigned a dose at least as high as the dose selected for the phase III study, and the NH study patients who are up to 30 months of age. In the case the model does not converge due to few number of patients, only descriptive statistics will be presented.

15 Safety analyses

15.1 Drug exposure

The scope of the drug exposure will include the preceding FIH study as well as the present study. The presentations will be based both on the extension study separately, and pooled with the preceding study.

For each patient, graphs will be produced displaying dose by time and accumulated substance over time.

Duration of exposure will be calculated for each patient. It is defined as the total number of days a patient is exposed to study drug, and will be calculated using the following formula:

Time on treatment (days) = [(Treatment end date) – (Treatment start date) + 1].

The duration (days) and amount (mg) of exposure as well as the area under exposure curve will be summarized in a table using summary statistics, including the number of patients, the mean, standard deviation, median, minimum and maximum.

15.2 Adverse events

An adverse event (AE) is defined as any untoward medical occurrence, including a clinically significant laboratory finding, symptom, or disease in a patient enrolled into this study regardless of its causal relationship to study drug.

A treatment-emergent AE (TEAE) is defined as any event not present before exposure to study drug or any event already present that worsens in either severity or frequency after start of treatment.

Adverse events will be coded using the latest version of Medical Dictionary for Regulatory Activities (MedDRA).

An overview table will present the following information.

- Number and percentage of patients reporting TEAEs
- Number and percentage of patients reporting serious TEAEs
- Number and percentage of patients reporting TEAEs leading to death
- Number and percentage of patients reporting TEAEs leading to study discontinuation
- Number and percentage of patients reporting TEAEs related to study drug

The number of events will also be displayed in this summary table.

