### **7.3.3 Withdrawal of patients from treatment or study**

#### **7.3.3.1 Withdrawal from treatment**

A patient should be withdrawn from the study treatment if, in the opinion of the investigator, it is medically necessary, or if it is the wish of the patient's primary caregiver(s). During the informed consent process, the investigator will clarify that it is essential for the patient's safety to be willing to comply with the study protocol requirements, including study safety and immunogenicity assessments following a potential withdrawal of study treatment.

When a patient is withdrawn from study treatment, the date and time of the last SOBI003 infusion and the date and reason for treatment withdrawal should be clearly described in the relevant sections of the case report form (CRF). If a patient is removed from treatment because of an AE, the reason for treatment withdrawal should always be stated as 'AE' irrespective of whether this was the investigator's or the patient's primary caregiver(s) decision.

After treatment withdrawal, efficacy, safety, immunogenicity and PK assessments should be completed as soon as possible and repeated 30 to 40 days after the last SOBI003 administration, as specified for "Early Termination" in the Schedule of Events (Table 2).

When possible, study assessments (excluding SOBI003 infusion) of Weeks 38, 52, 78 and 104 should continue in accordance with the Schedule of Events (Table 2) in order to collect continuous immunogenicity, safety and efficacy data for study patients following withdrawn treatment. Additional safety assessments will be performed at the discretion of the investigator, as warranted by the AE(s) leading to treatment withdrawal.

A patient that is withdrawn from study treatment due to an AE, should be followed up until the AE(s) leading to treatment withdrawal are either resolved or have stabilized even after the patient's participation in the study is over. Each clinically significant abnormal laboratory value or other clinically meaningful abnormality should be followed until the abnormality resolves or until a decision is made that it is not likely to resolve. Should the 30 to 40-day post last infusion be ADA-positive, then the ADA titer will be determined and ADA samplings will continue at approximately monthly basis until the ADAs have disappeared or titers have stabilized at a lower level. Every time an ADA sample is taken, a corresponding PK assessment is done.

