#### **7.3.3.2 Withdrawal from study**

The patient's legally authorized representative is free to withdraw the patient from the study at any time.

A patient that is withdrawn from the study should be examined as soon as possible, whenever possible, irrespective of the reason for withdrawal. The efficacy, safety, immunogenicity and PK assessments should be completed as soon as possible and repeated 30 to 40 days after the last SOBI003 administration, as specified for "Early Termination" in the Schedule of Events (Table 2). The CRF should be completed to the highest possible extent.

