**Table 2 Schedule of events – Overview Enrolment to End of Study**

Week	Enrolment and treatment period (Week 25 to 104)					ET a
	25	38	52	78	104/ END	
Informed consent	X					
Eligibility criteria	X					
Concomitant therapy	X					X
Physical examination b	X					X
Neurological examination			X		X	X
Height & head circumference			X		X	X
Weight c	X					X
Vital signs d	X					X
12-lead ECG			X		X	X
Antihistamine e	X					
SOBI003 administration f	X					
Adverse events	X					X
Anesthesia/sedation g for:						
CSF sampling (PK, ADA, HS)			X		X	
CSF sampling (future research) h			X		X	
MRI (brain, liver, spleen)			X		X	
Blood sampling for:						
Safety laboratory		X	X	X	X	X
Immunogenicity		X	X	X	X	X
HS		X	X	X	X	X
PK		X	X	X	X	X
Future research h			X		X	
Urine collection for:						
Safety laboratory (Dipstick)		X	X	X	X	X
HS		X	X	X	X	X
Actigraphy (sleep pattern) i			X		X	
BSID-III/KABC-II (neurocognition, language, motor function) j			X		X	X
Parent/caregiver questionnaires:						
VABS-II			X		X	X
CSHQ i			X		X	
PedsQL, incl. Family Impact Module			X		X	X

a In case of Early Termination (ET) of SOBI003 administrations, the assessments should be completed as soon as possible after decision of treatment withdrawal.

b General appearance and skin at the infusion site are examined prior to start of each infusion and within 1 hour of completion of each infusion. On Weeks 52 and 104, as well as at Early Termination, a complete physical

examination (general appearance, skin (including potential reactions around the infusion site), eyes, ears, nose, neck, lymph nodes, throat, heart, lungs, abdomen, musculoskeletal system and extremities) is conducted.

c During the treatment period, body weight is assessed at approximately 4-week intervals to determine the actual SOBI003 dose to be administered. Weight is therefore obtained prior to preparation of the SOBI003 infusions solution at Enrolment (Week 25) and every 4th week during the study. The weight is obtained either the day prior to the infusion or the day of infusion.

d Vital signs includes blood pressure, heart rate, body temperature, respiratory rate and oxygen saturation measured by pulse oximetry. At each infusion, assessments are done pre-infusion, mid-infusion and within 1 hour after end of infusion. If dose is adjusted, vital signs are measured according to 7.5.5.4.

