#### 7.5.1.8 Early withdrawal from treatment/study

If the patient is withdrawn from study treatment, the patient should be examined as soon as possible after making the withdrawal decision. AEs and use of concomitant medications are captured. Blood is collected for safety laboratory, HS, immunogenicity and PK assessments. Urine is collected for safety laboratory and HS assessments.

Vital signs are assessed, and a neurological and a physical examination are performed. An ECG is conducted, and height, weight and head circumference are obtained.

The VABS-II is assessed by parent/caregiver (refer to Section 7.5.3.2). The parent/caregiver completes the PedsQL questionnaire.

Based on the patient's developmental age, as determined by the VABS-II score, the BSID-III and/or KABC-II tests are conducted for assessment of neurocognition, language and motor function (see Sections 7.5.3.1, 7.5.3.2, and 7.5.3.6, respectively). If *both* BSID-III and KABC-II should be assessed, then the BSID-III should be administered 2 days prior to the completion of KABC-II.

When possible, study assessments (excluding SOBI003 infusion) of Weeks 38, 52, 78 and 104 should continue in accordance with the Schedule of Events. At minimum, the Early

Termination assessments should be repeated 30 to 40 days after the last SOBI003 administration. Patients with ADA-positive samples should continue to be followed in accordance with Sections 7.5.4.3 and 7.5.5.1.

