15.2.3 Adverse Events leading to study discontinuation

Treatment emergent AEs leading to study discontinuation will be summarized by system organ class and preferred term displaying the number and percentage of patients with at least one AE recorded at each level of summarization. The total number of events leading to study discontinuation and the number and percentage of patients with at least one treatment emergent AE leading to study discontinuation will also be displayed.

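### The SAP's two AE discontinuation counts are worded for leaving the study, so a child who stops SOBI003 for an AE but stays in follow-up is in neither count

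*SAP*

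**What the plan says.** **SAP.** The overview in 15.2 lists five items: any TEAE, serious TEAEs, TEAEs leading to death, "Number and percentage of patients reporting TEAEs leading to study discontinuation", and related TEAEs. Section 15.2.3 holds the only table devoted to discontinuation: "Treatment emergent AEs leading to study discontinuation will be summarized by system organ class and preferred term". Section 15.2.4 tabulates severity in three levels (mild, moderate, severe).

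**Protocol.** Section 7.3.3.1 deals with withdrawal from treatment. Where an AE is the cause, "the reason for treatment withdrawal should always be stated as" AE, whoever took the decision, and the CRF holds the date and reason. Such a patient "should be followed up until the AE(s) leading to treatment withdrawal are either resolved or have stabilized". The same section keeps the child under observation: "When possible, study assessments (excluding SOBI003 infusion) of Weeks 38, 52, 78 and 104 should continue in accordance with the Schedule of Events". Withdrawal from study has its own section, 7.3.3.2, which begins its instructions with "A patient that is withdrawn from the study should be examined as soon as possible". Table 12 grades AE severity from I to IV, with Grade IV for life-threatening consequences.

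**The concern.** The primary objective is long-term safety and tolerability, and protocol 5.2 warns that severe, even life-threatening, hypersensitivity or immune-mediated reactions may still occur. How many children had to stop SOBI003 because of an AE is one of the first things a reader of the report will look for. The SAP plans a count of a different event, leaving the study because of an AE. The protocol asks sites to keep these two events apart by retaining off-drug children. The better that request works, the lower the planned row becomes, and a low or zero figure could be taken as evidence of good tolerability. If the term stays undefined, two programmers could also fill the row differently from the same data.

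A smaller mismatch lies nearby. Without a Grade IV level, a life-threatening reaction would have to be shown as severe in the SAP's severity table.

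**Working it through.** The plan states no figure to reproduce. The check is a comparison of text, followed by simple proportions.

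**Step 1. Are the two events distinct in the documents?** Yes.
- The protocol gives them separate sections (7.3.3.1 and 7.3.3.2).
- Its rule on abnormal test findings (7.5.4.1.1) names withdrawal of the IMP and discontinuation from the study as alternatives.
- SAP 14.1 defines a turning point at which treatment stops and classifies assessments as before, at or after it.
- SAP 6 and 14.1.2 refer to patients who departed from the dosing scheme yet remained in the study.

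A child who is off drug and on study is therefore a case the plan foresees.

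**Step 2. Trace a child who stops SOBI003 for a TEAE and stays in follow-up.**

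| Output | Is the child counted? | Does it show that an AE ended treatment? |
|---|---|---|
| SAP 15.2, any TEAE | Yes | No |
| SAP 15.2, serious and related rows | If the event qualifies | No |
| SAP 15.2, study discontinuation row | No, as worded | Not applicable |
| SAP 15.2.3, table by SOC and preferred term | No, as worded | Not applicable |
| SAP 10, premature withdrawal with reasons | Unclear; it does not say from what | Unclear |
| SAP 15.1 exposure duration; 15.2.1 exposure and AE figures | Yes | No; timing only, without the reason |
| Protocol 9.4.7.1, listing of AEs leading to discontinuation | Probably; the term is unqualified | By patient, no count |
| SAP 9 patient listings; SAP 10 listing of withdrawal reasons | Yes, where recorded | By patient, no count |

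No specified summary clearly gives the number of children who stopped SOBI003 because of an AE.

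**Step 3. Size.** The planned number is n = 9 to 12 (protocol synopsis). One such child is 1/9 = 11.1%, 1/10 = 10.0%, 1/11 = 9.1% or 1/12 = 8.3% of the safety set.

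Let k be the number of AE-related treatment stops and j the number of those children who stay in the study. Then:
- treatment-withdrawal row = k/n;
- SAP row, read strictly = (k − j)/n;
- gap = j/n.

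The documents give neither k nor j. Taking k = 2 as an assumption:

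| n | k/n | SAP row, j = 0 | j = 1 | j = 2 |
|---|---|---|---|---|
| 9 | 22.2% | 22.2% | 11.1% | 0% |
| 12 | 16.7% | 16.7% | 8.3% | 0% |

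If j = 0, or if the row is read to include stopping treatment, the gap is zero.

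**Step 4. Severity.** Protocol Table 12 has four grades and SAP 15.2.4 has three levels, so Grade IV has no level of its own there. SAP 15.2.4 uses the same layout for treatment-emergent SAEs, so the grade is not visible in that version either.

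**The case against.** The strongest reply is that the SAP means the term loosely. The protocol itself sometimes merges the two events. The heading of 7.5.1.8 joins treatment and study, while its text begins "If the patient is withdrawn from study treatment, the patient should be examined as soon as possible after making the withdrawal decision". Footnote a of Table 2 ties early termination to the drug: "In case of Early Termination (ET) of SOBI003 administrations, the assessments should be completed as soon as possible". SAP 4.3.2 says patients receive SOBI003 to Week 104 unless withdrawn, which uses withdrawal in the sense of stopping treatment. This stands as a possible reading. The SAP does not adopt it, and it conflicts with the protocol's separate sections, so it is a reason to define the term.

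The second reply is that at 9 to 12 children the answer can be counted by eye from listings. That is largely true, and it limits the harm. It does not supply the planned count, and the protocol's listing does not say which kind of discontinuation it covers. SAP 5.2 refers to analyses identified in the protocol, but the sentence is about when analyses are run and does not define the row.

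Third, Grade IV events are not lost. Life-threatening events are serious under both documents and reach the SAE tables, and protocol 9.4.7.1 tabulates AEs by maximum severity under CTCAE grading. This stands, so only the mismatch in the SAP table remains.

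A reader might also infer more than the documents support:
- That such a child drops out of the AE overview. The child stays in the any-TEAE row and any other row that applies.
- That SAEs are missed because SAP 15.2.2 leaves out the protocol's criterion for medically important events. Investigators assign seriousness under the protocol definition, and no lost SAE is shown, so this is an editorial alignment only.

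**Conclusion.** The point holds as a reporting gap in the SAP. Its two AE discontinuation counts are worded for study discontinuation alone and, read as written, omit children who stop SOBI003 for an AE but remain in follow-up. Each omitted child is 8.3% to 11.1% of the planned sample. The primary endpoint, TEAEs and SAEs, is unaffected, and the underlying information is collected and listed. The size in practice depends on how many children stop for an AE and how many of them stay, which the documents do not give. If none does both, nothing changes.

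The text does not support a claim that safety data are lost or that the primary safety analysis is invalid. The change is still worth making before database lock, because the missing row bears directly on the tolerability part of the primary objective and costs little. The absent Grade IV level is a secondary mismatch confined to the SAP severity table.

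**What to change.** 1. Add to the SAP 15.2 overview a row for TEAEs leading to permanent withdrawal of SOBI003, separate from the study discontinuation row.
2. Split the premature-withdrawal row in SAP 10 into withdrawal from treatment and withdrawal from study, each with reasons. Protocol 7.3.3.1 already puts the reason and date of treatment withdrawal on the CRF.
3. Add a matching table by SOC and preferred term, or a listing, to SAP 15.2.3 if the AE page links each event to drug withdrawal. Check this first. Protocol 7.3.3.1 shows a reason at patient level only, and 7.5.4.1.3 names seriousness, causality and outcome but no such link.
4. Tabulate severity in SAP 15.2.4 by the protocol's Grades I to IV.
5. As an editorial alignment, bring the SAE wording in SAP 15.2.2 into line with protocol 7.5.4.1.1.

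The cost is SAP wording and a few table shells. Items 1 and 2 can draw on the CRF reason and date, and item 3 depends on the check above. The drawback is a little extra table work, with mostly small counts at 9 to 12 patients. No clinical rule changes.
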